2.4.2 POTENTIAL BENEFITS

Potential benefits resulting from this study:

• Information gained from the conduct of this study may be of benefit to other people with oropharyngeal dysphagia following stroke in the future.

The ideal patient population and treatment regimen for optimizing the use of pharyngeal electrical stimulation are still not completely understood now. However, most studies have demonstrated that patients with post-stroke dysphagia benefit to some degree from pharyngeal electrical stimulation when assessed using standardized measures of swallowing function and performance.

CONFIDENTIAL Page 28 of 71

Alternative treatments include other types of stimulation approaches (e.g., neuromuscular, direct neural, transcranial) for which there is little evidence for adoption into general practice. Patients will receive the standard interventions for dysphagia that are practiced at the participating institution and generally accepted by ASHA.

2.4.3 ASSESSMENT OF POTENTIAL RISKS AND BENEFITS

Post-stroke dysphagia in the hospital setting is associated with poor outcomes. It is known to increase the risk of life threatening and difficult to treat infections as well as increase mortality. If unresolved, dysphagia represents a major long-term disability burden, impacting patient survival, cost of care and quality of life. There are no clinically proven evidence-based treatments for dysphagia.

The Phagenyx® System is a NSR device. The safety profile associated with the use of the Phagenyx® System is well characterized by evidence accumulated from multiple clinical studies and ongoing post-market surveillance involving over 30 institutions in five countries over a period of 15 years. There are no characteristic device or treatment specific effects that are considered to be serious adverse events. The additional risks associated with the clinical study design are all well understood and can be easily mitigated. None of the protocol-specific assessments are expected to add significant risk over those risks inherent in the care of patients suffering dysphagia in the subacute stroke setting.

Patients participating in this study are expected to be exposed to only marginal incremental risk over standard of care, and some patients may experience more expedient and more successful outcomes associated with their dysphagia treatment. Hence, the benefits associated with study participation are expected to outweigh any incidental incremental risk.

CONFIDENTIAL Page 29 of 71

3 STUDY OBJECTIVES AND ENDPOINTS

STUDY OBJECTIVES	STUDY ENDPOINTS		
Primary			
To evaluate the efficacy of Phagenyx® treatment in reducing the severity of unsafe swallows.	Swallowing safety of a bolus based on PAS of each swallow, determined by a VFSS 48 hours after completion of investigational treatment, converted to a trichotomized ordinal response of safe (PAS 1-3), penetration (PAS 4-5), or aspiration (PAS 6-8). Each patient contributes up to 12 post-treatment repeated measurements (PAS) including 6 swallows of thin and 6 swallows of nectar.		
Secondary			
To evaluate the efficacy of Phagenyx treatment in improving nutritional management.	Functional Oral Intake Scale (FOIS) at 7 days following the last investigational treatment.		
	Dysphagia Severity Rating Scale (DSRS) at 7 days following the last investigational treatment		
Exploratory			

CONFIDENTIAL Page 30 of 71

STUDY OBJECTIVES	STUDY ENDPOINTS
To further characterize the efficacy of Phagenyx® treatment in reducing the severity of unsafe swallows.	The severity of unsafe swallows will be further evaluated via: O PAS outcome by each consistency (thin and nectar) O Physiologic measurement obtained using the Modified Barium Swallow Impairment Profile (MBSImP) metrics will be extracted from the thin and nectar swallows by the core lab by using the baseline and follow up VFSS data. These validated and reliable metrics of critical swallowing movements will be explored for their relationship to the primary study endpoint (PAS). O PAS dichotomized as safe (PAS 1-3) or
To evaluate the efficacy of Phagenyx® treatment on nutritional management changes.	unsafe (PAS 4-8) Nutritional management improvement will be evaluated via: Dysphagia Severity Rating Scale (DSRS) at 14 days or discharge, whichever is first, and at 11 weeks following the last investigational treatment. Time from baseline to removal of enteral feeding (i.e., removal of NG tube or PEG or transition to oral feeding, or first diet upgrade) Functional Oral Intake Scale (FOIS) at 7 days, 14 days or discharge, whichever is first, and 11 weeks following the last investigational treatment
To evaluate the efficacy of Phagenyx® treatment on improving quality of life.	Quality of life (QOL) will be assessed baseline and 11 weeks following the last investigational treatment via the following instruments: o EuroQoL-5 Dimension Questionnaire (EQ-5D) and EuroQoL-Visual Analogue Scale (EQ-VAS)

CONFIDENTIAL Page 31 of 71

STUDY OBJECTIVES	STUDY ENDPOINTS			
To evaluate the efficacy of	General stroke health outcomes will be			
Phagenyx® treatment on general	assessed by:			
stroke health outcomes.	 Time to discharge from site in which treatment is received Discharge destination from the site in which treatment is received Patient location (home, institution) at 11 weeks Days on antibiotics during hospital stay NIH Stroke Scale (NIHSS) at baseline and 14 days or discharge, and 11-week follow up Modified Rankin Scale (mRS) at baseline, 14 days, and 11 week follow up Barthel Index (BI) at baseline, 14 days or discharge, and 11-week follow up New onset pneumonia, using a standardized definition adapted from the STROKE-INF study²⁶ at baseline, 48 hrs, 7 days, and 14 days or discharge Hospital readmission rate Number of CXR (related to suspect pneumonia) 			

4 STUDY DESIGN

4.1 OVERALL DESIGN

This is randomized, sham-controlled, patient-masked, outcome assessor-blinded, prospective, multi-center study designed to support a *de novo* submission and FDA clearance for the Phagenesis Phagenyx® System for treatment of oropharyngeal dysphagia following a stroke. The study will follow an adaptive group sequential design with unblinded sample size re-assessment. To ensure 180 evaluable patients with 7-day data and assuming a 20% dropout rate, 225 patients will be enrolled initially. An interim analysis for futility will occur after the first 60 patients complete their 7-day visit and another interim analysis will be performed for efficacy after 120 patients complete their 7-day visit. The total sample size may be increased up to 338 patients after the second interim analysis to ensure 270 evaluable patients. Up to 15 investigational centers across the US and Europe will participate in this study. The enrollment period is expected to be approximately 24 months and patient participation will last for approximately 11 weeks. Patients will be assessed at the following intervals: baseline.

CONFIDENTIAL Page 32 of 71

within 48 hours of treatment, 7 days, 14 days or at discharge, whichever is first, and 11 weeks after completion of study treatments.

Investigational sites will be chosen from centers that have standardized protocols for treating patients with dysphagia post-stroke. Centers will be selected so that US sites represent the majority, with the ability to contribute at least 60% of the total patients. All sites must have speech language therapists/pathologists (SLT/SLP) on staff as well as affiliated VFSS facilities and personnel.

All enrolled patients will have the Phagenyx® Catheter placed and will receive either an active treatment with Pharyngeal Electrical Stimulation or a sham treatment by a HCP who is un-blinded to the treatment assignment.

Randomization will use stratification based on site and baseline PAS. Minimization may also be included to ensure group balance for study site and additional baseline covariates.

Administration of all protocol-specific assessments, other than PES or sham treatments, will be conducted by personnel who are blinded to the treatment assignment, including speech pathologists providing standard dysphagia care (excluding VitalStim and e-Stim). The standard dysphagia care data will be collected on the eCRF.

A core laboratory will be established for analysis of all procedural VFSS. The VFSS core lab will provide standardized baseline and follow-up analyses of the primary endpoint as well as VFSS-related tertiary endpoints. Personnel at the VFSS core lab will also be blinded to patient treatment assignment.

Up to three unblinded, active treatment roll-in patients will first be enrolled at each site in the US. The need for roll-in patients for European sites will be based on experience with the CE-marked device at the site and will be agreed to by Phagenesis and the site investigator. Roll-in patients will enable the site study staff to become fully proficient in the most effective way to administer the Phagenyx® treatment as well as perform other protocol-specific assessments. The sponsor will provide detailed training and education to the site staff in the use of the Phagenyx system and the protocol. The sponsor will provide an on-site representative to oversee and provide aid in the administration of PES during treatment of these roll-in patients. The sponsor will complete the Site Training and Competency Review form during the visit(s). The site will be approved to begin randomizing patients after the site meets the following competency requirements:

- The treatment administrator successfully and confidently completes up to three treatment sessions with little to no prompting or other aid from the sponsor representative,
- The treatment parameters recorded on the Base Station reflect appropriate stimulation levels, and
- Electronic case report forms (eCRFs) for baseline through the acute follow-up visit are completed correctly within 5 days of enrollment then within 5 days of each follow up for the roll-in patients.

CONFIDENTIAL Page 33 of 71

A formal review of site competency will be made after one to three roll-in patients have been treated, and the site is competent based on the above parameters. The site investigator and other relevant personnel will meet with sponsor personnel or their designee(s) via teleconference or on site to review the roll-in patient records and answer outstanding questions. The sponsor or their designee will provide approval to begin randomizing patients by controlling access to the randomization module of the study's EDC system. Meeting documentation including recommended actions and decisions will be retained in the eTMF for each site.

Roll-in patients will be analyzed independently from the primary analysis population but will not contribute to the sample size cap.

Dysphagic patients enrolled into the study will continue to receive enteral or oral nutrition via the same manner as prior to study entry and will also have the Phagenyx® Catheter placed as part of the study. In the US, patients may receive feeding through the Phagenyx® Catheter for up to 2 weeks as needed. In Europe, patients may receive feeding through the Phagenyx Catheter for up to 30 days.

4.2 SCIENTIFIC RATIONALE FOR STUDY DESIGN

Clinical investigation demonstrates that pharyngeal electrical stimulation holds potential for treating patients that are dysphagic following stroke. Based on the founding work reported by Fraser, cortical excitation is directly related to the amplitude of the stimulation signal. The outcome of the STEPS study (Bath et. al.²¹) had a neutral outcome, therefore, this study is designed to overcome some shortcomings that were noted in the STEPS study, including:

- Dysphagia entry criterion has been set to PAS ≥ 4 to limit mild dysphagia;
- Patients will be enrolled at least seven days after their index stroke to omit those with early spontaneous recovery;
- The sham treatment will include Phagenyx Catheter placement but *no* PES to prevent inadvertent treatment.

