The timing in the resolution of post-stroke dysphagia is also very difficult to estimate. There is a general belief that spontaneous resolution will occur within the first week to month, with only a few patients demonstrating persistent dysfunction beyond 6 months. Mann et. al.² set out to systematically define the true persistence at a single referral center in Australia. Sixty-five of 128 patients (51%; 95% CI, 42-60%) had a clinical presentation of dysphagia in the acute stroke setting. This incidence increased to 82 patients (64%; 95% CI, 55-72%) when videofluoroscopy was used to diagnose dysphagia. Follow up assessments were made at six months. Ninety-seven (97) of the 112 patients assessed at six months had returned to their pre-stroke diet (87%; 95% CI, 79-92%), but clinical evidence of swallowing abnormality remained in 56 patients (50%; 95% CI, 40-60%) and VFSS confirmed abnormalities in 51 (46%) with full aspiration in 17 (11%).

A number of researchers have similarly attempted to quantify the incidence of pneumonia, or "chest infection" in the post-stroke setting. Similar to studies of dysphagia incidence, published reports also lack standardization with respect to inclusion criteria, diagnostic methods and timeframes for reporting. Katzan et. al.,³ performed a large retrospective review of a 29-hospital-wide population cohort in the US to determine the incidence of pneumonia and its impact on 30-day mortality from 1991-

CONFIDENTIAL Page 15 of 71

1997. They report a 6.9% pneumonia incidence among 14,293 patients. Upon excluding patients that were dying or had Do Not Resuscitate orders within the first 3 days, the incidence became 5.6% out of 11,286 patients. Bivariate analysis between pneumonia and admission factors indicated that stroke severity (NIHSS score) and general indictors of frailty were predictors for pneumonia. No analysis for dysphagia was included.

Mann et al's study reported chest infections in 26 of 112 patients at 6-months (20%; 95% CI, 14-28%) with 12% of these occurring within the first month of stroke admission. Multivariate analysis demonstrated that the only independent predictor of chest infection was dysphagia².

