Twenty-eight (28) patients with unilateral hemispheric stroke were subsequently studied over their initial 3-month post-stroke course. Dysphagia was present in 71% of patients upon initial assessment and in 46% and 41% at one and three months, respectively. Cortical mapping of the motor pathways to the pharynx was performed at baseline and at one and three months using the methodology previously described. Non-dysphagic and persistently dysphagic patients showed little change in pharyngeal representation in either hemisphere at one and three months compared with baseline, but patients that recovered their swallowing function had an increased pharyngeal representation in the unaffected hemisphere at one and three months without change in the affected hemisphere. A functional reorganization of the brain by which swallowing control was transferred from the damaged hemisphere to the undamaged one was proposed as the mechanism of swallowing recovery.

[figure not shown]

Figure 2: Cortical reorganization associated with swallowing recovery. A) Typical cortical representation of swallowing motor cortex in a healthy individual; B) Typical cortical representation of swallowing function in a dysphagic patient who was thought to exhibit dominance in the right hemisphere; C) Typical cortical representation of patient who has recovered swallowing function: the dominance of control has moved to the left hemisphere.

Following the observation of this natural functional reorganization, Hamdy and colleagues began investigating the use of various sensory stimuli to drive this functional reorganization. Sensory inputs were tested (e.g., tactile, temperature, aversive taste) as well as experimental modes including transcranial direct current, magnetic field and electrical stimulation in the oropharynx (unpublished data). Transcranial magnetic stimulation was used to produce cortical maps based on evoked oropharyngeal motor responses to assess the cortical excitability in the motor centers associated with swallowing before and after each study intervention to assess the extent to which an intervention increased cortical activity. Pharyngeal electrical stimulation demonstrated promise. The rapid increase in cortical excitation after just ten minutes of stimulation is illustrated in **Figure 3**. Moreover, these changes persisted for 30 minutes after stimulation was discontinued thus suggesting that continuous stimulation was not necessary to facilitate reorganization¹⁶.

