The VFSS is considered the "gold standard" in the US for diagnosing the nature and severity of dysphagia as well as providing feedback on the effects of dysphagia therapy²¹. Hence, it would not be unusual for a dysphagic patient to undergo at least two VFSS studies over the course of being treated for dysphagia after stroke. The investigational protocol specifies two VFSS assessments be performed within a 1-week period to standardize baseline measures and to provide feedback on the dysphagia treatment under investigation shortly after the intervention. Patients typically undergo a non-instrumented dysphagia assessment before referral for an instrumented VFSS. Participating sites will be instructed to use the study-specific VFSS protocol for patients referred to an instrumented dysphagia assessment if they also appear to meet the rest of the study inclusion/exclusion criteria. Patients meeting the study criteria will require one subsequent VFSS performed according to the study-specific VFSS protocol. Hence, patients will be exposed to one, and possibly two, more VFSS than they would if they were not enrolled in this study.

The VFSS imparts a small dose of ionizing radiation. Zammit-Maempel et. al., reported a median exposure time of 171 seconds and an associated dose of 0.20 milliSieverts or mSv⁴³, while Moro and Cazzani reported a median exposure time of 149 seconds and

CONFIDENTIAL Page 26 of 71

an associated dose of $0.35~\text{mSv}^{44}$. The standardized VFSS protocol proposed for this study is associated with an average duration of 2.9 minutes radiation exposure (95% confidence interval 2.8-3.0 minutes). Extrapolating from the relationship Moro and Cazzani published, the VFSS time of 2.9 min (174 sec), relates to an effective dose of $\sim 0.44 \text{mSv}^{45}$.

Table 1 provides background information on relative average absorbed doses of ionizing radiation that a person would experience when exposed to various sources. On average, a U.S. resident receives an annual radiation exposure from natural sources of about 3.1 mSv. In addition, man-made sources of radiation from medical, commercial and industrial activities contribute roughly 3.1 mSv more to our annual exposure⁴⁶. Computed tomography (CT) scans, are among the largest of these sources, with a head CT contributing 2mSv⁴⁷.

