5 STUDY POPULATION

5.1 INCLUSION CRITERIA

CONFIDENTIAL Page 34 of 71

To be eligible to participate in this study, an individual must meet all of the following criteria:

- 1. Age \geq 18 and \leq 90 years.
- 2. Acute ischemic or hemorrhagic cerebral stroke within 7-28 days of baseline VFSS.
- 3. Score of 0 or 1 on NIHSS question 1a, Level of Consciousness.
- 4. *Moderate to severe dysphagia (PAS ≥4) on baseline VFSS (Baseline VFSS must meet the threshold criteria of demonstrating a PAS of ≥ 4, in three of the six boli (5 mL/1 tsp/bolus), during swallowing "thin liquid" barium media as assessed by the clinical staff administering the VFSS) unless its deemed too high risk then only 2 swallows will qualify.
- 5. Willing and able to have the Phagenyx® Catheter placed transnasally.
- 6. Willing and able to provide informed consent.
- 7. Stated willingness to comply with all study procedures and availability for the duration of the study.

*Note that the baseline VFSS will include testing with both thin liquids (up to 6 swallows) and nectar liquids (up to 6 swallows). For inclusion criterion 4, only the thin liquid swallows on the baseline VFSS will be considered. However, for descriptive statistics and other analyses, both the thin liquid and nectar liquid swallows on the VFSS will be considered.

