2.2. Study Schema

2.3. Randomization Methodology

Randomization will be stratified by site and baseline PAS. Within each stratum a minimization approach with probabilistic allocation (Pocock and Simon, 1975) will be used to optimize balance between treatment groups on key prognostic factors including NIHSS, baseline PAS, and age. Randomization will occur via the study's EDC system. Administrative permission to access the randomization module and randomization eCRF will be limited to unblinded HCPs who will administer treatment and who will monitor study compliance.

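### Time from stroke is not a named balancing factor or a term in the primary and DSRS models, a small loss that is nearly free to mend; the one-week VFSS interval needs reconciling.

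*Protocol*

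**What the plan says.** Protocol 4.2 lists design changes made in response to a neutral earlier trial of the same treatment. One is the entry floor: "Patients will be enrolled at least seven days after their index stroke to omit those with early spontaneous recovery". Inclusion criterion 2 (Protocol 5.1) sets the window: "Acute ischemic or hemorrhagic cerebral stroke within 7-28 days of baseline VFSS".

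On natural history, Protocol 2.1 reports: "There is a general belief that spontaneous resolution will occur within the first week to month". Protocol 2.3.1 describes 28 patients with unilateral hemispheric stroke: "Dysphagia was present in 71% of patients upon initial assessment and in 46% and 41% at one and three months, respectively".

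On allocation, SAP 2.3 states: "Randomization will be stratified by site and baseline PAS". Minimisation within strata is meant to "optimize balance between treatment groups on key prognostic factors including NIHSS, baseline PAS, and age". Protocol 4.1 and 6.3 allow further baseline covariates in the minimisation but name none.

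On analysis, SAP 4.8 gives these terms (its subsections are numbered 4.6.1 and 4.6.2):
- **Primary GEE:** treatment, bolus consistency, baseline maximum PAS, and treatment by consistency.
- **FOIS:** a CMH test stratified by site and baseline PAS.
- **DSRS ANCOVA:** treatment, center, baseline PAS and baseline DSRS.

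SAP 4.3.4 plans no covariate adjustment and SAP 4.3.6 plans no subgroups.

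On the two swallow studies, the radiation text in Protocol 2.4.1 says: "The investigational protocol specifies two VFSS assessments be performed within a 1-week period". Protocol 5.1, 8.1.3 and the schedule of activities do not repeat that interval. SAP 4.3.9 applies no visit windows, and SAP 4.3.1 defines baseline as the latest measurement before treatment, whatever its age.

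**The concern.** The protocol treats spontaneous recovery as a threat and answers it with a floor at day 7. Its own figures show that most of the three-month decline in dysphagia has happened by one month, and the entry window overlaps that month. Time from stroke is therefore a plausible prognostic factor, and the trial must already know it to apply inclusion criterion 2. Yet nothing in the plan commits to balancing it or adjusting for it in the primary or DSRS analysis.

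If one arm happened to enter somewhat earlier after stroke than the other, part of the difference in swallowing or diet could reflect natural recovery, in either direction. Variation in outcome that a known baseline value could explain would also stay in the error term.

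The VFSS interval is a related but separate matter. The baseline PAS is the adjuster in the primary model, so its age matters, and the only text that limits its age indirectly is in a risk section.

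**Working it through.** **1. The plan's own figures.** 180/0.80 = 225 and 270/0.80 = 337.5, rounded up to 338; both reproduce. The SAP 4.2 odds ratio of 2.23 gives a design log odds ratio of ln(2.23) = 0.802. The stated power of 95% (primary) and 85% (both endpoints) came from simulation. It cannot be rebuilt, because category rates and within-patient correlation are not given. Nothing below depends on it.

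**2. When the decline occurs (Protocol 2.3.1).** By one month: 71 - 46 = 25 points. By three months: 71 - 41 = 30 points. Share by one month: 25/30 = 83%. The series does not date the initial assessment or split days 0-7 from days 7-28. A constant rate would put about 73% of the first-month decline after day 7, but the data allow any share from 0 to 100%.

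**3. A slope from the same figures.** logit(0.71) - logit(0.46) = ln(0.71/0.29) - ln(0.46/0.54) = 0.895 + 0.160 = 1.056.
- Spread over 30 days: 1.056/30 = 0.035 per day, or 0.25 per week.
- All within the 21 days from day 7 to day 28: 1.056/21 = 0.050 per day, or 0.35 per week.

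This assumes that the prevalence of dysphagia and the odds of a safer swallow change at the same logit rate.

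**4. Chance imbalance.** Assume entry uniform over days 7-28, 1:1 allocation and simple randomisation. SD = 21/sqrt(12) = 6.06 days. The SE of the difference in arm means is 6.06 x sqrt(4/N).

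| N | 95% range for imbalance, days |
|---|---|
| 120 | +/-2.17 |
| 180 | +/-1.77 |
| 270 | +/-1.45 |

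At N=180, 1.77 x 0.035 = 0.06 and 1.77 x 0.050 = 0.09 log odds. Against 0.802 that is 8% to 11%.

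**5. Precision.** Uniform entry over three weeks has variance 3²/12 = 0.75 weeks². With an assumed between-patient SD of 2.0 logits (variance 4), the share explained is about 0.25² x 0.75/4 = 1.2% to 0.35² x 0.75/4 = 2.3%. A simulation (1,500 trials per setting, 180 patients, 12 swallows each, patient-mean score with and without days since stroke) gave effective sample size ratios of about 1.00, 1.03 and 1.10 at slopes of 0.2, 0.5 and 0.8 logits per week. Interpolating the first two gives 1.005 at 0.25 and 1.015 at 0.35. Both routes point to roughly 1-2%.

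**6. The VFSS interval.** Session 3 is about 2 days after session 1 (Protocol 6.1.3). The follow-up VFSS is 24-72 hours after the last session. First treatment to second VFSS is therefore 2 + 1 = 3 to 2 + 3 = 5 days. If both exams fall within 7 days, the gap from baseline VFSS to first treatment is at most 7 - 5 = 2 to 7 - 3 = 4 days. Protocol 2.4.1 thus implies a limit. Criterion 2 and the schedule, read alone, would admit a VFSS on day 8 with first treatment on day 22. The two exams would then be 14 + 3 = 17 to 14 + 5 = 19 days apart, contrary to Protocol 2.4.1.

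**The case against.** The case against acting is strong on size. Allocation is randomised against a concurrent sham, so recovery is non-differential in expectation, and the test's error rate already allows for chance imbalance. The floor removes the first week on purpose, and entrants must still show PAS of at least 4 on repeated thin boluses, which selects persistent dysphagia. The natural-history series is small: 41% is not a whole number out of 28 (11/28 = 39%, 12/28 = 43%), so the denominator apparently changed, and the step from one to three months rests on about two patients. The minimisation list, "key prognostic factors including NIHSS, baseline PAS, and age", is open, and SAP 4.8 lets exploratory models use unnamed prognostic covariates. All of this stands. It limits the size of the point, but none of it commits the primary GEE or the DSRS ANCOVA to time from stroke.

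A reader might infer more than the documents support:

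- **That the gap from baseline VFSS to treatment has no limit.** Protocol 2.4.1 implies about 2-4 days. The defect is that the interval is stated in one place only.
- **That a day-7 entrant is on the steep part of the curve and a day-28 entrant on the flat part.** Over six days, the month-one average rate, ln(71/46)/30 = 0.0145 per day, gives about 8% recovery; the later rate, ln(46/41)/61 = 0.0019 per day, gives about 1%. But the later rate applies only after one month and describes almost no one entering at days 7-28. The series cannot show how the rate varies within the window.
- **That adjustment would gain 10% in sample size.** That needs 0.8 logits per week; the protocol's figures imply 0.25-0.35.
- **That baseline PAS is redundantly used in SAP 2.3.** Stratum cut-points are not given, so minimisation may balance PAS within coarse strata.

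**Conclusion.** The point holds as a small, nearly free improvement and a reconciliation item. Time from stroke is plausibly prognostic on the protocol's own evidence, and neither the named allocation factors nor the primary and DSRS models include it. This does not threaten validity: the documents support no claim of systematic bias.

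The size is that of steps 4 and 5: a chance imbalance worth at most about a tenth of the design effect, and a precision gain of a percent or two. Those figures rest on uniform entry, simple randomisation, a slope borrowed from a 28-patient prevalence series, and an SD of 2.0 logits that the documents do not supply. The simulation used a patient-mean score, not the planned ordinal GEE. No comparable figure can be given for DSRS, because the documents offer no slope of DSRS on time from stroke.

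The VFSS interval is an inconsistency between sections. It is not evidence that old baseline exams will be used.

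**What to change.** 1. In SAP 4.8, add days from stroke to randomization as a prespecified covariate in the primary GEE and the DSRS ANCOVA, and use the same models at the interim and final analyses. Amend SAP 4.3.4 to agree. The value is a baseline one, obtainable from the stroke date needed for inclusion criterion 2 and the randomization date in the EDC system. Days to first treatment session should not be used, since it is fixed only after randomisation and is undefined for patients never treated. Naming days from stroke as a minimisation factor in SAP 2.3 is optional.
2. Reconcile Protocol 2.4.1 with Protocol 5.1, Protocol 8.1.3, the schedule of activities and the SAP on the interval between the two VFSS exams, so that all say the same thing.

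The covariate costs SAP wording and no new data collection; it should be settled before any unblinded look. The optional minimisation factor would need an EDC change. The second item costs a protocol clarification; its effect on recruitment depends on how the sponsor resolves it.
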